An analgesic alternative with few associated limitations is **pulsed electromagnetic field (PEMF)** therapy, also called pulsed short-wave therapy, pulsed radiofrequency energy therapy, and radiofrequency nonthermal diathermy.¹ Over the last 7 decades, PEMF has been used to treat acute and chronic pain, decrease inflammation and edema, and hasten wound healing and bone regeneration.¹ Possible mechanisms for the multiple clinical effects of PEMF are multifactorial, complex, and only partially understood.¹ The primary theory involves the promotion of calcium binding to calmodulin which activates endothelial and neuronal nitric oxide synthase isoforms, producing nitric oxide which has anti-inflammatory and analgesic effects, among other consequences

[figure not shown]
such as decreasing edema while increasing blood and lymph flow.¹

[figure not shown]
In 1947, the United States Federal Communications Commission assigned three frequencies for radiofrequency use in medical treatments: 40.68, 13.56 and 27.12 MHz.¹ Within just a few years, the first pulsed electromagnetic field generator was cleared by the United States Food and Drug Administration for use with patients using 27.12 MHz: the Diapulse.^{2,3}. Until relatively recently, available devices consisted of a large signal generator and bulky coil applicator that were not portable and produced significant electromagnetic interference, making them impractical for common use (Figure, right). However, over the past 70 years they have exhibited an extraordinary safety profile: these are noninvasive, nonpharmacologic devices, with no side effects, adverse events, or medication interactions; and the only

contraindications are pregnancy and an implanted pulse generator such as a cardiac pacemaker. Unlike opioids, there is no risk of abuse, dependence, and/or diversion.

More recently, small, simple, lightweight, battery-powered, noninvasive PEMF devices have received FDA clearance for use treating acute and chronic pain, including the ActiPatch and RecoveryRx for amputees and the initial 150 surgical subjects of Phase I (Model 088, BioElectronics, Frederick, Maryland; **Figure, below left**); as well as SofPulse for the subsequent 80 surgical subjects of Phase II (Endonovo Therapeutics, Woodland Hills, California; **Figure below right**). We will be using the devices for FDA-approved indications; in other words, on-label use.

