9. RESEARCH DESIGN AND METHODS

This will be a single-center (UCSD), randomized, participant- and observer-masked, sham-controlled, parallel-arm human subjects pilot study.

Enrollment. Participants will be consenting adults either (1) undergoing various surgical procedures usually resulting in moderate-to-severe postoperative pain, or (2) experience post-amputation phantom and/or residual limb pain. Study inclusion will be proposed (1) to eligible presurgical patients or (2) after an amputee contacts the investigators. If an individual desires study participation, written, informed consent will be obtained using a current UCSD IRB-approved ICF. The study population of interest includes adult women and men of all races, ethnicity, sexual identity, and socioeconomic status. Inclusion and exclusion criteria are listed in section #10 below.

Procedures. Following written, informed consent, we will record baseline anthropometric information (age, sex, height, weight, amputation details and current pain levels). Surgical participants will receive any standard peripheral nerve block(s) administered using bupivacaine or ropivacaine 0.5% with epinephrine (standard at UCSD) prior to undergoing their surgical procedure *per standard of care*.

Treatment Group Assignment. Each participant will be randomized to one of two treatment groups: *Active* or *Sham* treatment. For the initial 150 subjects of Phase I, there are sham RecoveryRx devices produced that are identical to active RecoveryRx devices, only they do not deliver PEMF. Randomization will be stratified by surgical procedure/amputation, in block sizes of 2. The computer-generated randomization lists will be created by the University of California San Diego Investigational Drug Service in a 1:1 treatment group ratio using opaque envelopes. For the initial 150 subjects of Phase I using RecoveryRx devices, the active and sham devices are indistinguishable in appearance, and therefore investigators, participants, and all clinical staff other than the individual who opens the randomization envelope and chooses a sham or active device will be masked to treatment group assignment for the duration of the data collection period. For the subsequent 80

subjects of Phase II, active SofPulse devices will be provided to patients randomized to the active treatment group; and sham RecoveryRx devices will be provided to the patients randomized to the sham treatment group.

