Study intervention. For surgical patients of Phase I, the PEMF device (2 devices, if there are multiple incisions or the incision is larger than the device diameter; 3 devices for total knee and hip arthroplasty or spinal surgery) will be affixed over the primary wound area(s) using tape and activated prior to recovery room discharge (*Experimental*). For surgical patients of Phase II, a single PEMF device will be used for each participant due to their larger diameter and treatment area. For amputees, the device used is over-the-counter (ActiPatch, BioElectronics, Frederick, Maryland) and 2 devices (both the same treatment group) will be shipped to the patient either in or out of California who will then contact an investigator for assistance in self-placement of the device on the residual limb. The optimal location to treat phantom pain is currently unknown and will partially informed by the results of this pilot study, and patients will be encouraged to move the devices to a new anatomic location every two days until relief is experienced.

Supplemental analgesics. In addition to the PEMF device(s), participants will receive standard-ofcare supplemental analgesics which can include acetaminophen, ibuprofen, ketorolac, opioids, gabapentin (this is provider- and patient-dependent). *Therefore, all patients of this study—regardless* of the treatment arm they are randomized to—will continue to receive current usual and customary analgesia: all will receive the same combination of supplemental analgesics they would regardless of study participation (of note, amputees will be asked to continue their normal analgesic regimen, including any as-needed treatments). Participants (and their caretakers of surgical patients) will be provided with verbal and written instructions, and the telephone and pager numbers of an investigator available during business hours throughout the treatment period. Participants can shower with the device in place, but not submerge it during swimming or a bath, as advised by the manufacturer.

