10. HUMAN PARTICIPANTS

We will recruit a convenience sample with a maximum of **270 participants in total (all participants who sign an informed consent included)**. Selection for inclusion will not be based on race, ethnicity, sexual identity, or socioeconomic status. There will be no participants from vulnerable populations, such as pregnant women, children, or prisoners.

Inclusion criteria (amputees): Adult patients of at least 18 years of age [19 years in Alabama and Nebraska], (1) with an upper or lower limb amputation at least 12 weeks prior to enrollment distal to the shoulder or hip (femoral head remaining), respectively, and including at least one metacarpal or metatarsal bone, respectively; (2) who experience at least moderate residual and/or phantom limb pain—defined as a 3 or higher on the Numeric Rating Scale (NRS; 0-10, 0= no pain; 10=worst imaginable pain)—at least daily for the previous 2 months; and (3) willing to avoid both changes to their analgesic regimen as well as elective surgical procedures for 70 days after initiation of treatment with PEMF therapy.

Inclusion criteria (surgical patients): Adult patients of at least 18 years of age undergoing one of the surgical procedures listed below:

- a. non-mastectomy breast surgery with a single-injection paravertebral nerve block
- b. laparoscopic or open cholecystectomy
- c. laparoscopic sleeve gastrectomy
- d. percutaneous nephrolithotomy
- e. ventral hernia repair
- f. inguinal hernia repair
- g. knee or hip arthroplasty
- h. foot/ankle surgery with at least moderate pain anticipated
- i. shoulder acromioclavicular joint repair, labral repair, subacromial decompression, or Bankart repair (without rotator cuff repair)
- j. hand/forearm/elbow/shoulder surgery with at least moderate pain anticipated
- k. spinal surgery with at least moderate pain anticipated

Exclusion criteria: (1) concurrent use of an implanted pulse generator (e.g., cardiac pacemaker); (2) pregnancy; (3) incarceration. **Surgical participants only:** (4) chronic opioid/tramadol use (daily use within the 2 weeks prior to surgery and duration of use > 4 weeks); (5) neuro-muscular deficit of the surgical area/limb; (6) a planned postoperative perineural local anesthetic infusion.

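### Amputees who already use a PEMF device are eligible and their use is not recorded, so some may be on active PEMF during the sham period

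*Combined protocol and SAP*

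**What the plan says.** Section 9 (Study intervention) states: "For amputees, the device used is over-the-counter (ActiPatch, BioElectronics, Frederick, Maryland". Section 7 describes such devices as cleared for the condition these participants have: "small, simple, lightweight, battery-powered, noninvasive PEMF devices have received FDA clearance for use treating acute and chronic pain".

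Section 10 gives three exclusions that apply to amputees: "1) concurrent use of an implanted pulse generator (e.g., cardiac pacemaker); (2) pregnancy; (3) incarceration". The remaining items, starting with "4) chronic opioid/tramadol use (daily use within the 2 weeks prior to surgery and duration of use > 4 weeks", are for surgical participants only, and none of them concerns PEMF. The amputee inclusion criteria do not mention PEMF use before enrolment either. Criterion (3) asks that participants be "willing to avoid both changes to their analgesic regimen as well as elective surgical procedures for 70 days" from the start of treatment.

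Section 9 (Supplemental analgesics) adds that "amputees will be asked to continue their normal analgesic regimen, including any as-needed treatments". Neither statement makes an exception for a PEMF device. The baseline information listed in section 9 is "age, sex, height, weight, amputation details and current pain levels", and the assessment table has no row for PEMF use.

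**The concern.** Aim 2 (section 6) is to estimate the effect of adding PEMF to usual analgesia, as a basis for sizing later trials. For an amputee who already uses a PEMF device, PEMF is part of usual care, and active versus sham no longer tests its addition. That person may receive active PEMF from their own device while assigned to sham, and duplicate PEMF while assigned to active.

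The amputee outcomes of primary interest are the change in average residual and phantom limb pain from baseline to Day 28 of the initial treatment, and the Patient Global Impression of Change on that day. Use of an own device can affect both ends of the pain change. Because of the crossover, every amputee has a sham period, so a current user contributes a contaminated one whichever order they are assigned. With PEMF history absent from the data, the analysis could neither identify these participants nor set them aside in a sensitivity analysis.

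**Working it through.** The plan states no amputee sample size, power or prevalence of PEMF use, so there is no figure to reproduce. The check is a reading of the text, followed by an illustration of size.

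**Step 1. Is a current user eligible?** The device can be obtained outside the trial (section 9). No exclusion for amputees and no amputee inclusion criterion refers to PEMF (section 10). A current user with pain of 3 or higher, at least daily for the previous 2 months, therefore qualifies.

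**Step 2. Does the regimen text remove the problem?** It depends on whether an own PEMF device counts as part of the analgesic regimen. The plan does not say.

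| Reading | Current user at entry | Buying a device during the 70 days |
|---|---|---|
| PEMF is part of the regimen | Stopping would be a change, so use continues | Barred as a change |
| PEMF is not part of the regimen | Not addressed | Not addressed |

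The first reading has some support: section 7 introduces PEMF with "An analgesic alternative with few associated limitations is pulsed electromagnetic field (PEMF) therapy". Under neither reading does the plan keep a current user's own device out of the sham period.

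**Step 3. Can the user be found at analysis?** No. Neither the baseline list nor the assessment table contains the information.

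**Step 4. Size.** Let p be the share of amputees who use their own active device throughout (an assumption). Suppose their mean outcome U is the same on active as on sham, and let A and S be the active and sham means in everyone else. With randomization, p is equal in the two arms in expectation:

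- Active mean = (1 - p)A + pU
- Sham mean = (1 - p)S + pU
- Difference = (1 - p)(A - S)

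For a later trial with the SD unchanged, the required sample size scales as 1/(1 - p)². Starting from a nominal two-sided 0.05 test with 80% power, power becomes Φ[(1 - p)(1.960 + 0.842) - 1.960].

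| Assumed p | Effect retained | Sample size factor | Power, from nominal 80% |
|---|---|---|---|
| 0.02 | 0.98 | 1/0.98² = 1.04 | Φ(0.786) = 78.4% |
| 0.05 | 0.95 | 1/0.95² = 1.11 | Φ(0.702) = 75.9% |

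For a given p this is the worst case, because it assumes continuous use and no remaining contrast in users. Intermittent use would lose less. The power column is an illustration for a future trial, since the pilot has no powered amputee comparison.

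**The case against.** The strongest reply is that the regimen text is about drugs. The Supplemental analgesics paragraph names only medications and describes them as given on top of the study device, and the request to continue the normal regimen sits in that paragraph. A reader might infer that the rule requires current users to keep their own device running. The documents do not say so: it is one possible reading. This part of the objection stands, but it does not close the gap, because on the drug-only reading own-device use is simply not addressed.

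The reply continues that few people are affected. Section 7 says PEMF is not in wide use, and the pain criterion screens out users whose pain is well controlled. This also stands, and it is why the range above stops at 5%. A loss of a fifth would need one amputee in five to be a current user, which nothing in the documents supports. A count of affected participants cannot be given either. No amputee target is stated, and the 270 in section 10 is a maximum that counts everyone who signs consent.

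A reader might also infer that recent users who still have pain are non-responders who lower the estimate. The documents do not support that direction. Such a person may have responded and relapsed after stopping, responded in part, or used the device too briefly.

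Finally, this is an exploratory pilot, randomization balances users in expectation, and any bias is towards no effect. All true, but balance between arms does not prevent dilution, and the effect estimate is what the pilot exists to supply.

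**Conclusion.** The concern holds as a modest gap in the amputee eligibility criteria and data collection. The explicit list of criteria admits current PEMF users, nothing keeps their own device out of the sham period, and the data could not show who they are. The likely consequence is a slightly diluted active-sham contrast: 2% to 5% of the effect at an assumed p of 0.02 to 0.05. This rests on two assumptions: the share of users, for which the documents give no figure, and the complete loss of contrast in those users. The conclusion is confined to amputees and to current use. The documents give no basis for extending it to surgical participants, and excluding past users would be a matter of preference.

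**What to change.** Four changes, all for amputees only:

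1. Section 10, exclusions: add current use of a PEMF or pulsed short-wave device other than the study device.
2. Section 10, inclusion criterion (3): add willingness not to use a non-study PEMF device during the 70 days.
3. Section 9, Supplemental analgesics: reconcile the sentence on continuing the normal regimen with the two changes above, stating whether non-study PEMF devices fall within it.
4. Section 9, baseline data: record prior PEMF use. This is preferable to a look-back exclusion because it keeps past users in the sample, and Aim 2 seeks to learn which amputee characteristics suit the treatment.

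The cost is one screening question, a few sentences of wording, and the loss of the few candidates who currently use such a device.

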14. POTENTIAL RISKS

There are currently no known medical risks from PEMF, although there is the risk of an allergic reaction to the tape used to hold the device to the skin. There is the risk of loss of confidentiality. The following study procedures will be done to maintain confidentiality of this study: hard copies will be kept in locked medical offices and the locked Investigational Drug Service's files. Any digitized records containing personal health information will be stored as password-protected and encrypted files.

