18. RISK/BENEFIT RATIO

There are no known medical risks of PEMF therapy, although there is the risk of allergic reaction from the tape used to secure the device to the skin. With its ease of application, lack of side effects, prolonged duration of action, and simple removal, PEMF therapy has the very real possibility of replacing opioid analgesics—the standard of care for the past 100 years—that would completely revolutionize postoperative analgesia, as we know it.

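### No eligibility criterion or screening question covers a known tape or adhesive allergy, the only physical risk the protocol names: a minor participant-safety gap

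*Combined protocol and SAP*

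**What the plan says.** Section 14 (Potential Risks) states: "There are currently no known medical risks from PEMF, although there is the risk of an allergic reaction to the tape". The only other risk listed there is loss of confidentiality. Section 18 (Risk/Benefit Ratio) repeats it: "There are no known medical risks of PEMF therapy, although there is the risk of allergic reaction from the tape".

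Section 10 (Human Participants) has six exclusion criteria. Three apply to everyone: "1) concurrent use of an implanted pulse generator (e.g., cardiac pacemaker); (2) pregnancy; (3) incarceration". Three apply to surgical participants only: "4) chronic opioid/tramadol use (daily use within the 2 weeks prior to surgery and duration of use > 4 weeks", then "5) neuro-muscular deficit of the surgical area/limb; (6) a planned postoperative perineural local anesthetic infusion".

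Section 15 (Risk Management Procedures) discusses pregnancy and implanted pulse generators. It describes no known theoretical hazard from either and presents both exclusions as precautionary. It does not mention tape.

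On wear, section 9 says that devices for Phase I surgical patients are taped over the wound area before recovery room discharge. Removal is planned after Day 8 for SofPulse and after Day 30 for ActiPatch and RecoveryRx, and participants may take devices off from Day 7. Amputees receive devices by mail and place them on the residual limb themselves with an investigator's assistance. Of the amputees, section 9 also says that "patients will be encouraged to move the devices to a new anatomic location every two days until relief is experienced". They then repeat the protocol with the opposite treatment from Day 35.

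**The concern.** The protocol takes precautions against two hazards that it regards as essentially theoretical and none against the one physical hazard that it treats as real. The risk management section does not follow up the only physical risk listed in the section just before it. A candidate who already knows that tape or adhesive gives them a skin reaction meets every criterion as written and can be asked to wear a taped device, active or sham.

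What is at stake is avoidable exposure of a small number of people. For amputees no in-person check of the skin is described, because recruitment, consent and device delivery are remote. Since the pilot is meant to optimize the protocol for later definitive trials, the omission could also be carried forward. This point concerns who is enrolled. Whether skin reactions are recorded during follow-up is a separate matter.

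**Working it through.** No plan figure needs reproducing. The check is a comparison of sections, followed by two short calculations of size.

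1. **Risk named.** Sections 14 and 18 agree: the tape is the one physical risk.

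2. **Exclusions.** Of the six criteria in section 10 (pulse generator, pregnancy, incarceration, chronic opioid use, neuromuscular deficit, planned perineural infusion), 0 of 6 concern tape, adhesive or skin allergy.

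3. **Inclusions.** The amputee criteria cover age, amputation level and timing, pain severity, and willingness to avoid analgesic changes and elective surgery. The surgical criteria cover age and procedure. None concerns tape.

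4. **Risk management.** Section 15 covers two contraindications, neither of them tape.

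5. **Screening steps.** Section 11 has surgical candidates' electronic records reviewed and a call made. Amputees contact the team by email or telephone before receiving consent forms. Neither step includes a tape or adhesive question.

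6. **Planned exposure (section 9).**
   - Phase I surgical: up to 30 days per device.
   - Amputees: up to 30 days per device in each of two periods.
   - Phase II: a treatment period described as 8 days.
   - Removal is allowed from Day 7.

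7. **How many people.** The documents give no allergy rate. Assume that 1% to 3% of candidates know they react to tape. Section 10 sets a ceiling of 270, counting everyone who signs consent.
   - 0.01 × 270 = 2.7
   - 0.03 × 270 = 8.1

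   That is about 3 to 8 people. It is an upper figure, because 270 is a maximum and not everyone who signs need be taped.

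8. **Effect on the estimate.** Only active-arm participants who lose exposure can dilute the effect. Take the worst case, in which affected participants get no treatment at all, and use the Phase II planning values in section 9: a 33% reduction from a sham mean of 23.9, with an SD of 12.3.
   - Target difference: 0.33 × 23.9 = 7.89 points
   - Dilution at 1%: 0.01 × 7.89 = 0.08 points (0.08 / 12.3 = 0.006 SD)
   - Dilution at 3%: 0.03 × 7.89 = 0.24 points (0.24 / 12.3 = 0.019 SD)
   - Active participants affected, taking the stated 70 in a 1:1 ratio: 35 × 0.01 = 0.35 to 35 × 0.03 = 1.05

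   This is negligible.

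**The case against.** The best defence is that this is a drafting omission about an accessory. Pregnancy and pulse generators are excluded because they are the contraindications to the studied energy; tape is only a means of fixing, so leaving it off the list does not contradict the protocol. Staff already review surgical records and correspond with amputees, so a known severe allergy may well surface. Section 7 says the device works through clothing or a bandage, so tape directly on skin is not shown to be essential. The risk is disclosed in the protocol, and what the consent form says cannot be checked here. Some would add that a pilot can usefully learn how ordinary candidates tolerate the fixing.

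Much of this stands as a limit on severity. It does not remove the gap: no section requires the question to be asked, informal detection is not a criterion, and disclosure is not screening.

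Several stronger readings are tempting and are not supported:

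- **Bias toward no effect.** A reader might infer that reactions distort the treatment estimate. At the assumed rate the loss is 1% to 3% of the effect at worst, and the surgical outcomes of primary interest cover only the first 7 days, so later reactions cannot touch them.
- **Forced removal.** The documents do not say that a participant who reacts must take the device off.
- **Thirty days for the Phase II sham arm.** This can be inferred from the use of sham RecoveryRx devices, but section 9 describes the Phase II treatment period as 8 days.
- **About 15 tapings per amputee device.** Moving every two days for 30 days gives 30 / 2 = 15 only if relief never comes. The relocation text does not itself mention tape, and a new site shortens contact at any one place.
- **Two devices per amputee in total.** Section 9 ships two devices for the first period alone.

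**Conclusion.** The concern holds as a minor participant-safety gap. The protocol names tape allergy as its only physical risk, and none of its six exclusions, its inclusion criteria or its risk management text screens for it, so people with a known reaction are eligible as written. That part rests on the text alone and needs no assumption.

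The number affected is unknown; about 3 to 8 of 270 is an upper illustration that depends wholly on the assumed 1% to 3% and on affected people enrolling as readily as others. There is no material consequence for power, bias or analysis. The case for change is that the exposure is avoidable at very little cost.

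**What to change.** Reconcile sections 10, 14, 15 and 18. Add one criterion to the exclusions that apply to all participants: known allergy or previous significant skin reaction to medical tape or adhesive. Add a matching sentence to section 15 so that the named risk has a stated precaution. Check it at the record review or call already described for surgical candidates, and at the first contact with amputees (both in section 11).

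The cost is one line of eligibility text and one screening question, with no extra visit, test or staff. A few otherwise eligible people are lost, and their number cannot be stated from the documents. Because the 270 ceiling counts people who have signed consent, asking before consent uses up none of those places.
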